2.4 RT Dose Rationale

RT to a measurable metastatic site will be delivered at a dose of 7.5 Gy X 3 (22.5 Gy total dose), given consecutively on days 1-3-5, by intensity modulated radiotherapy (IMRT) and/or image guided radiotherapy (IGRT) techniques, to best spare the normal tissue. The choice of this fractionation regimen of RT is based on the NYU preclinical experience of radiation and ipilimumab [61], that suggests superiority of the 8 Gy x 3 fractions regimen (for a total dose of 24 Gy) to induce abscopal effects in murine cancer models. In humans, the biological equivalent can be calculated by applying the linear quadratic model [62] to determine which dose delivered in 3 fractions would result in comparable tumor control to that of the standard regimen of 3 Gy x 10 fractions (total dose 30 Gy) commonly used in the clinic to palliate metastatic disease. The α/β is a tissue and effect-specific parameter associated with this conversion model, which α/β is taken to be 10 Gy for cancer metastases [63-65]. As demonstrated in Table 1, the closest equivalence is achieved by 7.5 Gy x 3, which explains the choice for this trial. Importantly a 3 fraction regimen is very user-friendly (only 3 visits to radiation oncology). Both UCLA and WCM are equipped to provide Intensity Modulated RT (IMRT) and, if necessary Image guided RT (IGRT), if the site targeted is close to vital organs.

Table 1. Biologically effective dose (BED) for different fractionation regimens of radiotherapy

	8 Gy x 3	6 Gy x 5	7 Gy x 3	7.25 Gy x 3	7.5 Gy x 3	3 Gy x 10 standard dose
($\alpha/\beta = 10$ Gy)	43.2	48	35.7	37.5	39.4	39

2.5 Risk/Benefit Assessment

The currently available information on the toxicology profile of LY2157299 is quite favorable, and the dose and fractionation of radiotherapy used in this study is unlikely to be associated with severe side effects. Thus the combination represents a viable alternative for metastatic breast cancer patients interested in investigational immunotherapy approaches.

2.6 Correlative Studies Background

2.6.1 *TGF β gene response signature*

A well-defined and robust TGF β gene response signature (TBRS) [66] was strongly associated with three specific subsets of human breast cancer [67]. These findings suggest that the TGF β pathway is activated in particular breast cancer subgroups and may predict for response to TGF β neutralization, a concept that will be tested in this study. We plan to assess TGF β gene response signature (TBRS) positivity in primary tumors (from blood cells and formalin-fixed and paraffin-embedded archival tissue samples) as predictive biomarker of response to LY2157299 plus radiation therapy combination therapy. Based on past experience, we assume that approximately 50% of subjects will have TBRS-positive tumors. Subjects who have TBRS-positive tumor and derive clinical benefit will be considered true positive. Sensitivity, specificity, positive and negative predictive value will be estimated.

2.6.2 *Circulating levels of TGF β*

As a biomarker, many studies have suggested that circulating TGF β levels provide an index of tumor response to RT and may predict normal tissue toxicity. We will monitor circulating levels of TGF β prior to, during and after radiation therapy in patients with metastatic cancer before and after LY2157299 treatment. Measuring TGF β presents several challenges. First, TGF β is produced and circulates in a latent form that is abundant, but its activity is highly regulated and short-lived. Second, the low levels of active TGF β present in serum can easily be obscured by the potentially high background of TGF β unintentionally released by platelet degranulation in specimens. Lastly, most methods require exogenous latent TGF β activation by acid or heat, which compromises the simultaneous detection of other cytokines. These factors contribute to erratic measurements by most commonly used assays, including the widely used ELISA. We will measure TGF- β 1 levels in EDTA and/or CDTA from collected plasma utilizing an ELISA design developed by Lilly Research Laboratories.

2.6.3 *Tumor-specific immune responses*

Tumor-specific responses will be assessed initially in HLA-A2+ cells that will be re-stimulated ex vivo with sur1M2 survivin peptide and additionally, for HER2neu positive tumors, the HER: p369-377 peptide. Non-HLA-A2 patients will be tested using peptides immunodominant for their

known HLA type. Quite a range of known epitopes is available [68-69]. While it is unrealistic to expect that all responses will be detected with equal sensitivity as this is influenced by the binding avidities, positive longitudinal responses to any peptide with time after treatment would indicate significant responses. In a follow-up assay, if sufficient PBMCs are available, the ability of LY2157299 plus RT to alter the hierarchy of the response and to determine whether responses to all epitopes are equally affected will be tested using HLA-A2+ PBMCs that respond to sur1M2 survivin but with 4 distinct survivin peptides [70]. We anticipate that LY2157299 plus RT will enhance tumor-specific immune responses and cause epitope spreading in the majority of patients.

2.6.4 Levels of circulating Tregs

The levels of circulating Tregs will be evaluated in patients. Tregs are especially relevant for the study because of their relative radiation resistance and because of the importance of TGF- β in their generation and function. Because the composition of PBMCs changes during cancer treatment [71], it is important that Treg levels are assessed both as a % of CD4 cells, as a % total lymphocytes, % total PBMCs, and as absolute counts. The assay can be performed at the same time as tetramer staining and on the same sample if necessary (7), enabling the assessment of lymphocyte representation in one sample and the determination of CD4:CD8 T cell ratios. Since Tregs are radiation resistant, if significant differences in response are found between patients, efforts could also be made to correlate changes with dose volume histograms obtained during RT. It is anticipated that Treg numbers and function will decrease in patients receiving LY2157299 plus RT, in particular in those who show enhanced tumor immunity and demonstrate abscopal anti-tumor effects. In general, RT increases Treg activity, but it is expected that LY2157299 will counter this effect allowing immune activation.

3. SUBJECT SELECTION

3.1 Study Population

Patients must have biopsy proven metastatic breast cancer and who have stable disease or progressed after at least one course of chemotherapy or hormonal therapy. In addition, patients

must have at least 3 metastases with at least one measurable metastatic lesion and who meet the inclusion and exclusion criteria will be eligible for study participation.

3.2 Inclusion Criteria

- 3.2.1 Biopsy proven breast carcinoma which is persistent and metastatic or recurrent and metastatic.
- 3.2.2 Patients must have failed at least one line of chemotherapy for metastatic disease.
- 3.2.3 Patients who are HER2+ as defined by ASCO CAP guidelines must have failed all prior therapy known to confer clinical benefit
- 3.2.4 Patients must have at least 3 distinct metastatic sites with at least one measurable lesion which is at least 1 cm or larger in largest diameter.
- 3.2.5 At the time of enrollment, patients must be ≥ 4 weeks[‡] since all of the following treatments (and recovered from the toxicity of prior treatment to \leq Grade 1, exclusive of alopecia):
 - major surgery;
 - radiotherapy;
 - chemotherapy (note: must be ≥ 6 weeks since therapy if treated with a nitrosourea, mitomycin, or monoclonal antibodies such as bevacizumab);
 - immunotherapy;
 - Biotherapy/targeted therapies.
([‡] - Patients can begin two weeks from prior treatment if they are asymptomatic from previous therapy)
- 3.2.6 Patient ≥ 18 years of age.
- 3.2.7 Patient life expectancy > 6 months.
- 3.2.8 ECOG status of 0 or 1
- 3.2.9 Adequate organ function including:
 - a) Marrow: Hemoglobin ≥ 10.0 g/dL, absolute neutrophil count (ANC) $\geq 1,500/\text{mm}^3$, and platelets $\geq 100,000/\text{mm}^3$.
 - b) Hepatic: Serum total bilirubin $\leq 1.5 \times$ upper limit of normal (ULN)
(Patients with Gilbert's Disease may be included if their total bilirubin is ≤ 3.0 mg/dL), alanine aminotransferase (ALT), and aspartate aminotransferase (AST) $\leq 2.5 \times$ ULN. If the patient has known liver metastases, an ALT and/or AST $\leq 5 \times$ ULN are allowed.
 - c) Renal: Estimated or measured creatinine clearance ≥ 60 mL/min.
 - d) Other: Prothrombin time (PT) and partial thromboplastin time (PTT) $<$ ULN.
- 3.2.10 Patients must have negative tests (antibody and/or antigen) for hepatitis

viruses B and C unless the result is consistent with prior vaccination or prior infection with full recovery.

- 3.2.11 Male and female patients of child-producing potential must agree to use effective contraception while enrolled on study and receiving the experimental drug, and for at least 3 months after the last treatment.
- 3.2.12 Ability to understand and the willingness to sign a written informed consent document. Patients may not be consented by a durable power of attorney.

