Short Title:	LY2157299 and Radiotherapy in Metastatic Breast Cancer
Clinical Phase:	Phase II
Principal Investigator:	[name], M.D.
Sample Size:	N= 28 (WCM will enroll a total of 18 patients and UCLA will enroll 10 patients)
Accrual Ceiling:	35
Study Population:	Patients must have biopsy proven metastatic breast cancer and have stable disease or progressed after at least one course of chemotherapy or hormonal therapy. This study will not enroll vulnerable population. Women > 18 years and < 90 years.
Accrual Period:	3 years
Study Design:	TGFB blockade will enhance response of irradiated tumors and improve the function of Dendritic and T cells. Patients will receive 300 mg/day of study drug administered via oral drug tablet every day for 14 days on and 14 days off (=28 day cycle). Radiation to a metastatic site will be delivered at a dose of 7.5 Gy, given consecutively on days 1-3-5.
Study Duration:	Study participation will involve 15 visits over the course of 16 weeks (approx.4 months). Patients will have an annual follow-up up to 5 years.
Study Agent/	
Intervention Description:	LY2157299 will be administered oral drug tablet: 300mg/day. Patients will receive 300 mg/day of study drug administered via oral drug tablet every day for 14 days on and 14 days off (=28 day cycle) .
Primary Objective:	1. to assess safety and feasibility of combining TGFβ receptor I kinase inhibitor LY2157299 and local radiotherapy 2. To determine if treatment with TGFB receptor I kinase inhibitor LY2157299 and localized RT achieves an abscopal tumor regression;
Secondary Objectives:	1. to estimate the local response rate of combining TGFB receptor I kinase inhibitor LY2157299 and local radiotherapy 2. To determine if treatment with TGFB receptor I kinase inhibitor LY2157299 and localized RT enhances tumor-specific immunity in

patients with metastatic breast cancer, and if this is associated with abscopal tumor regression.

3. To determine if treatment with TGFB receptor I kinase inhibitor LY2157299 and localized RT alters the numbers and function of T-reg cells in patients with metastatic breast cancer.

Endpoints:

Primary Endpoint: A. To assess safety and feasibility of combining TGF β receptor I kinase inhibitor LY2157299 and local radiotherapy
B. To determine if treatment with TGFB receptor I kinase inhibitor LY2157299 and localized RT achieves an abscopal tumor regression

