Secondary Endpoint: A. *to estimate the local response rate of combining TGF β receptor I kinase inhibitor LY2157299 and local radiotherapy,*

B. to determine if treatment with TGF β receptor I kinase inhibitor LY2157299 and localized RT enhances tumor-specific immunity in patients with metastatic breast cancer, and if this is associated with abscopal tumor regression.

C. to determine if treatment with TGF β receptor I kinase inhibitor LY2157299 and localized RT alters the numbers and function of T-reg cells in patients with metastatic breast cancer.

SCHEMA

Patients with metastatic breast cancer receiving at least one single agent chemotherapy and demonstrating stable disease or disease progression at two consecutive clinical/radiological assessments (at an interval of at least 2 weeks). Stable disease is defined as: < 30% decrease in the sum of the longest diameter (LD) of target lesions, taking as reference the baseline sum LD or < 20% increase in the sum of the LD of target lesions without the appearance of one or more new lesions. After obtaining informed consent:

Baseline CT and PET scan

Definition of target and non-target lesions: **Non-target** lesion is treated by radiation while **Target** lesions are followed to assess possible abscopal effect

[figure not shown]

TABLE OF CONTENTS

Protocol Summary	12
SCHEMA.....	14
1. STUDY OBJECTIVES	18
1.1. Primary Objectives.....	18
1.2. Secondary Objectives.....	18
2. BACKGROUND.....	18
2.1 TGF β.....	18
2.1.1 TGF β in Oncology: Rationale for Blocking TGF β signaling Therapy.....	20
2.2 Investigational Agent or Device	21
2.2.1 Pharmacokinetics and Pharmacology	21
2.2.2 Preclinical Studies	24
2.2.3 Toxicology Studies	24
2.2.4 Clinical Experience with LY2157299	25
2.3 Rationale	26
2.4 RT Dose Rationale	27
2.5 Risk/Benefit Assessment	27
2.6 Correlative Studies Background.....	28
2.6.1 TGF β gene response signature	28
2.6.2 Circulating levels of TGF β	28
2.6.3 Tumor-specific immune responses	28
2.6.4 Levels of circulating Tregs	29
3. SUBJECT SELECTION.....	29
3.1 Study Population.....	29
3.2 Inclusion Criteria.....	30
3.3 Exclusion Criteria.....	31
4 REGISTRATION PROCEDURES.....	33
4.1 General Guidelines	33
4.2 Patient Registration Process	33
5.1 Investigational Agent or Device Administration.....	34
5.2 Pretreatment Evaluations.....	34
5.3 On-Study Evaluations	35
5.4 General Concomitant Medication and Supportive Care Guidelines ...	37
5.5 Duration of Therapy	37
5.6 Duration of Follow Up.....	37

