5. TREATMENT PLAN

5.1 Investigational Agent or Device Administration

Enrolled patients will receive 300 mg/day of LY2157299. LY2157299 will be administered as an oral drug tablet.

The study drug will be administered orally on a 28-day cycle (1 cycle=28 days), every 2 weeks, or 14 days on / 14 days off. Blood samples will be obtained at baseline, and weeks 2, 6 and 15 for immune monitoring. Imaging by PET/CT or CT(Chest/Abdomen/Pelvis) will be performed at baseline, 5 weeks and 15 weeks. The chosen metastatic sites will receive conformal external beam radiation 7.5 Gy/fraction x 3, to a total of 22.5 Gy over the course of one week (on alternating days):

- lesion 1 will be irradiated at week 1 (RT starts 1 day after 1st dose of LY2157299),
- lesion 2 will be irradiated at week 5 (RT starts after 1stdose of the second cycle of LY2157299)

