11 MEASUREMENT OF EFFECT

Abscopal responses will be assessed at 15 weeks based on [78] (Table 2). This choice of this interval is to enable a sufficient length of study to detect abscopal responses. In fact, the experience in the clinical trials of Ipilimumab in melanoma demonstrated occasional initial progression of disease with appearance of new metastatic sites when compared to the baseline imaging assessment. “Flares” at the first PET/CT or CT(Chest/Abdomen/Pelvis) assessment were often followed by clinical responses to the antibody. While the mechanism of action of

Ipilimumab is different from that of LY2157299, the experience with TGF β inhibition in malignant glioma reported by Hau et al [79] confirms the lesson from the melanoma trials, i.e. that whenever the response is mediated by the immune system the following course is likely to manifest: 1) achievement of a clinical and radiological measurable response is slower than that of a typical response to cytotoxic therapy (RT or chemotherapy); 2) it can be heralded by an initial “flare” or emergence of new metastatic sites and, 3) with time it may be dramatic and would have been missed if the drug was discontinued too soon [80] [81].

Table 2: Immune response criteria (irRC)

	Summary of irRC
Note:	New, measurable lesions are incorporated into tumor burden
CR	Disappearance of all index and non-index lesions in two consecutive observations not less than 4 weeks apart, without the development of any new lesions.
PR	$\geq 50\%$ decrease in tumor burden compared with baseline in two observations at least 4 weeks apart
SD	50% decrease in tumor burden compared with baseline cannot be established nor 25% increase compared with nadir
PD	At least 25% increase in tumor burden compared with nadir (at any single time point) in two consecutive observations at least 4 weeks apart

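### Eligibility does not secure an unirradiated measurable lesion, so an eligible patient could have no target lesion for the abscopal co-primary endpoint

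*Combined protocol and SAP*

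**What the plan says.** **Eligibility.** Section 3.1 says patients "must have at least 3 metastases with at least one measurable metastatic lesion". Section 3.2.4 has the same minimum with a size: "Patients must have at least 3 distinct metastatic sites with at least one measurable lesion which is at least 1 cm or larger". Neither mentions irradiation.

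**Radiotherapy.** The three descriptions differ.
- Protocol Summary, Study Design: "Radiation to a metastatic site will be delivered at a dose of 7.5 Gy". This is one site, with nothing on measurability.
- Section 2.4: "RT to a measurable metastatic site will be delivered". This is one site, and it is measurable.
- Section 5.1: "The chosen metastatic sites will receive conformal external beam radiation", with lesion 1 treated in week 1, and "lesion 2 will be irradiated at week 5". This is two lesions, with nothing on measurability.

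**Endpoint.** The Schema separates irradiated (non-target) lesions from target lesions at baseline, and the target "lesions are followed to assess possible abscopal effect". Section 11.1.3 makes every measurable, unirradiated lesion a target and refers to Table 2 for abscopal response. In Table 2 a partial response is a fall of at least 50%: "decrease in tumor burden compared with baseline in two observations at least 4 weeks apart". Section 11.1.1 names the immune response criteria at 15 weeks as the primary endpoint. Section 11.1.2 classes bone lesions, effusions and several other kinds of disease as non-measurable.

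**Analysis.** Section 14.1.2 A puts every treated patient in the efficacy analysis. Section 14.1.2 B tests a rate of at most 0.05 against 0.19 in 28 patients, and three or fewer responses mean rejection. It allows up to 56 enrolments to obtain 28 evaluable at 15 weeks. The Protocol Summary gives an accrual ceiling of 35.

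**The concern.** The entry criteria and the endpoint definition do not meet. Entry guarantees one measurable lesion. The endpoint needs one that is both measurable and unirradiated. The three-site rule does not bridge this, because the other two sites may be bone lesions or effusions, which cannot be targets.

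A patient with no target has a baseline sum of zero, and a 50% decrease from zero is undefined. Table 2's complete response does mention non-index lesions, but the only non-target rule, section 11.1.4.2, is headed as being for irradiated lesions. Section 14.1.2 keeps the patient in the efficacy analysis without saying how to count the patient or whether being evaluable requires a target lesion. A single such patient matters slightly, because the decision rests on reaching 4 responses in 28. The safety and feasibility co-primary is not touched.

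**Working it through.** **Step 1. Lesion count.** Take three sites, the minimum at entry.
- One measurable, two non-measurable: irradiating the measurable one, as section 2.4 describes, leaves 0 targets. Sparing it, as section 5.1 permits, leaves 1.
- Two measurable, one non-measurable: irradiating both measurable lesions under section 5.1 leaves 0.
- Three measurable: irradiating two leaves 1.

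No target is therefore possible but not inevitable. The exclusion criteria (3.3), registration steps (4.1, 4.2) and pretreatment evaluations (5.2) do not require a target lesion. The Schema text has lesions classified at baseline but does not make a target a condition of entry. The Schema figure is not shown.

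**Step 2. Reproduce the design.** With X ~ Binomial(28, p) and success at X ≥ 4:
- P(X ≥ 4 | 28, 0.05) = 0.049
- P(X ≥ 4 | 28, 0.19) = 0.807

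The stated alpha of 0.05 and power of 80% are reproduced. The sample size is correct as calculated.

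**Step 3. Affected patients kept among the 28 as non-responders.** Let f be the share with no target lesion. The documents give no value for f, so 5% and 10% are assumptions. Also assume that 0.19 (and 0.05 under the null) is the rate among patients who have a target. The rate in all treated patients is then 0.19 × (1 − f), and 0.05 × (1 − f) under the null.

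| f | Rate under alternative | Power | Rate under null | Type I error |
|---|---|---|---|---|
| 0 | 0.19 | 0.807 | 0.05 | 0.049 |
| 5% | 0.1805 | 0.770 | 0.0475 | 0.042 |
| 10% | 0.171 | 0.729 | 0.045 | 0.035 |

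With exactly one patient who cannot respond, 27 can: P(X ≥ 4 | 27, 0.19) = 0.782, and P(X ≥ 4 | 27, 0.05) = 0.044.

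**Step 4. Affected patients replaced.** Power stays at 0.807. Expected enrolment is 28/(1 − f):
- f = 5%: 28/0.95 = 29.5, about 30
- f = 10%: 28/0.90 = 31.1, about 32

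Both lie below the ceiling of 35 in the Protocol Summary and the 56 in section 14.1.2 B.

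**The case against.** The best reply is that the plan, read as a whole, already points to sparing the measurable lesion. Section 5.1 treats two chosen sites out of at least three. Section 11.1.4.2 scores irradiated lesions by disappearance, persistence or clear progression plus markers, with no measurement, so the natural purpose of the one-measurable-lesion criterion is to supply the target. The Schema sorts lesions into the two classes at baseline. An investigator would have to irradiate the only lesion able to show the efficacy endpoint, and section 2.4 is a dose rationale, not the operative treatment text. This is plausible and makes the problem less likely. It does not close the gap: no visible passage states it, and section 2.4 points the other way. Because the Schema figure is missing, the absence can be asserted only for the visible text.

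Three stronger readings are tempting, and the documents do not support them.
- **The trial is underpowered.** The stated design reproduces, f is unknown, and if 0.19 already describes all eligible patients, including any without a target, no power is lost.
- **Replacement would exhaust the enrolment limit.** At 5–10% it does not, under either limit. The disagreement between 35 and 56 is a separate matter.
- **Such a patient could not be assessed at all.** Section 11.1.3 also has uptake values determined for each lesion and scored by PET criteria. Those are not the primary measure in section 11.1.1, and CT without PET is permitted, so they do not rescue the co-primary endpoint.

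**Conclusion.** The gap is real but limited: the entry criteria do not guarantee the lesion on which the abscopal co-primary is measured, and the plan does not say how a patient without one is counted. Severity is minor to moderate.

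Its size cannot be established from the documents, and the affected share may be near zero. The illustrative loss is about 2 points of power for one affected patient, 4 points at 5% and 8 points at 10%. It depends on two assumptions: that 0.19 applies to patients with a target lesion, and that affected patients stay among the 28 as non-responders. The error is in the conservative direction, since type I error falls as well. A reader might infer a risk of a false positive result; on these assumptions there is none.

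**What to change.** 1. Amend sections 3.1 and 3.2.4 to require at least one measurable lesion that is planned to remain unirradiated and is recorded as a target lesion at baseline.
2. State in section 14.1.2 that a treated patient without a target lesion counts as a non-responder in the all-treated analysis, and whether such a patient is one of the 28 evaluable at 15 weeks.
3. Reconcile the Protocol Summary, section 2.4 and section 5.1 on the number of irradiated sites and whether they must be measurable. This point takes no view on which site is treated.

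The text change is small and applies to patients still to be enrolled. The cost is that patients with no such lesion become ineligible and their safety and immune data are lost. Accrual slows a little. At the 4 eligible patients per month in section 14.1.2 B, 28 patients take 28/4 = 7.0 months with no loss, 28/(4 × 0.95) = 7.4 months at 5% and 28/(4 × 0.90) = 7.8 months at 10%. That is the same time to 28 patients with a target lesion as enrolling and replacing affected patients.
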